**Table 9: Product Matrix and Nominal Sirolimus Dosages**

Implant Option	Components	Implant Area (cm  )	Dose (µg)	Total Implant Area (cm  )	Total Dose (µg)
A	AF3010 + VF1520	3 + 3	225 + 225	6	450
B	AF3010 + VF2020	3 + 4	225 + 300	7	525
C	AF3010 + VF1530	3 + 4.5	225 + 337.5	7.5	562.5
D	AF3010 + VF2030	3 + 6	225 + 450	9	675

Product implantation instructions are provided in the Instructions For Use (see [Appendix C](#)) enclosed with each SeCI component membrane package.

## 9.2. Subject Enrollment

### 9.2.1. Index Procedure

The conduct of the AV fistula creation surgery, including type of anesthesia and the surgical technique must be documented. The technical components of the surgery include the type of suture used for the anastomosis, method used to occlude arterial inflow and outflow, etc.

**Hydrostatic distension of the vein and use of rigid dilators to size or probe the vein is permitted, however, balloon dilation of the vein is not permitted.** The immediate pre-operative and intra-operative medications administered as part of the surgical procedure will be documented. These medications include heparin and any topical vasodilators.

Once the surgeon declares patency of the newly constructed fistula and that hemostasis is satisfactory, the surgical outcome is judged to be successful and the subject will be eligible for enrollment in the study. Confirmation of successful AV fistula creation will be determined by the presence of a palpable thrill and any one of the following:

- a satisfactory auditory signal using a handheld Doppler, or
- visual augmentation of the juxta-anastomotic segment following application of a proximal tourniquet, or,
- verification of fistula patency using duplex ultrasound

**Should the AV fistula creation procedure fail, the subject will be considered a screen failure.**

## **9.2.2. Treatment Assignment**

The designated surgical coordinator will retain control of the investigational product during the conduct of the index procedure. Until use, the investigational product must be kept in a controlled area with limited access and the tamper evident seal must not be broken until treatment assignment.

### **9.2.2.1. Run-in Subjects**

The first subject eligible for enrollment under each participating surgeon at each investigational site in the study will receive the SeCI. The designated surgical study coordinator will break the tamper evident seals, the surgical team will prepare the product per instructions provided in the Instructions for Use (see [Appendix C](#)), and the surgeon will implant the investigational product.

### **9.2.2.2. Randomization**

Following successful creation of an AV fistula, subjects will be randomized in a 1:1 ratio to treatment or control using permuted block randomization stratified by surgeon and fistula location (radiocephalic / brachiocephalic). At least 80% of the subjects randomized will receive a radiocephalic fistula and at most 20% of the randomized subjects will receive a brachiocephalic fistula. The above randomization scheme will be applicable to subjects on hemodialysis at the time of enrollment or not on hemodialysis at the time of enrollment separately. The randomization scheme will be monitored and controlled via the IVR/IWR system.

The designated surgical study coordinator will contact the IVR/IWR System to receive the randomization code and treatment assignment for the subject.

- If the subject is randomized to the treatment group, the designated surgical study coordinator will break the tamper evident seals, the surgical team will prepare the product per instructions provided in the Instructions for Use (see [Appendix C](#)), and the surgeon will implant the investigational product.
- If the subject is randomized to the control group, the surgeon will complete the surgery per standard practice, (without implanting the investigational product). The designated surgical study coordinator will ensure that the tamper evident seals on the investigational product packaging have not been broken and will return the investigational product to inventory.

Following completion of surgery, the designated surgical study coordinator will confirm using the IVR/IWR System that:

- the surgical procedure was successfully completed, and,
- the randomization number was used

Once a randomization number has been used, it will not be re-used. Authorized study personnel will ensure that the assigned randomization number is recorded in the subject's source document.

Upon completion of the index procedure, the surgical incision will be closed according to the surgeon's standard practice.

If the subject is randomized to the control group, the designated surgical study coordinator will ensure that the tamper evident seal on the component membrane packaging has not been broken and will return the investigational product to inventory.

### **9.2.3. Blinding/Unblinding**

This study is a single-blind investigation since it will not be possible to blind the implanting surgeon, the designated surgical coordinator, operating room staff, and unblinded monitor with respect to the assigned treatment group.

Blinded personnel include but are not limited to the subject, the nephrologist, the staff at the dialysis centers, and the sponsor and/or designee who handle study monitoring, data management, and analysis.

An individual with knowledge of the randomization code/treatment assignment will not exclusively participate in decisions relating to fistula outcomes (e.g., fistula maturation/non-maturation, determination of fistula abandonment, need for supplementary interventions, etc.).

In case of an emergency, when knowledge of the actual treatment becomes medically necessary, a blinded investigator will be able to obtain details of the treatment assigned to an individual subject. The Medical Monitor will be immediately informed that the blind needs to be broken who will then authorize the blind to be broken and treatment assignment disclosed to the blinded investigator. Under no circumstances will the blind be broken prior to notification and consent of the Medical Monitor.

Any direct verbal or written communication regarding treatment identification beyond what is required at an institution for the recording of the surgical procedure is prohibited.

The post-operative note in the hospital chart, the official surgical report, as well as the letter to the referring MD will include the usual description of the AV fistula surgery along with the statement "subject is participating in investigational study protocol VT-304". ***There will be no reference made as to whether the subject received the investigational implant product or not.*** The randomization code that was assigned to the subject (without details about the subject's treatment assignment) will also be recorded in the source document.

The unblinded surgical study coordinator will maintain the subject's treatment assignment in an Overall Accountability Log in a secured, controlled area that has restricted access. The carton containing the investigational product will include a 6-part label with space provided for the subject's number, initials and the assigned randomization code. The surgical study coordinator will place this label on the Overall Accountability Log for future accountability. An unblinded monitor will perform the accountability review (see Section 9.5).

### **9.3. Packaging and Labeling**

Each component membrane of the Sirolimus-eluting Collagen Implant is a sterile, single-use only product, packaged in an amber vial, which is stored in a Tyvek pouch. The Tyvek pouch is the primary sterile barrier. The Tyvek pouch is packaged in a foil pouch. The foil pouch is placed within a carton. The product is gamma sterilized and is non-pyrogenic. Each carton contains one (1) component membrane.

Each component of the product (amber vial, foil pouch, and carton) is labeled with the following information: product name, component code, size, lot number, storage conditions, sponsor's identification and address, and the statement, "Caution: New Drug – Limited by Federal (or United States) law to investigational use."

Each package contains a 6-part label, which includes the following information: product name, component code, and lot number. One section should be removed and placed on the appropriate Accountability Log for study product accountability.

### **9.4. Storage Conditions**

The SeCI supply must be stored in the original packaging between 2°C and 8°C (36-46°F) in a secured, controlled area with restricted access.

### **9.5. Accountability**

In accordance with ICH-GCP, the investigational site will account for all investigational supplies throughout the study. Details of receipt, storage, administration, and return of the SeCI will be recorded in an Overall Accountability Log provided by the sponsor and/or designee. The Overall Accountability Log will be maintained by the Surgical Study Coordinator in a secured, controlled area that has restricted access. An unblinded monitor will perform all functions related to drug accountability in order to maintain the blind throughout the study.

### **9.6. Return and Destruction**

After an unblinded monitor has performed final accountability and the investigator and/or designee have reconciled any discrepancies, all unused investigational supply will be returned to the sponsor. Documentation of the returned investigational supply will accompany the shipment and a copy will be kept at the site. The site will not destroy any used or unused investigational supply unless the sponsor provides written authorization to the contrary.

In the event of a potential defect in the quality of investigational supply, the sponsor may initiate a recall procedure. In this case, the investigator will be responsible for promptly addressing any request made by the sponsor to recall investigational product.

## 9.7. Concomitant Medications

Information on concomitant medications must be collected from the time of screening up to the 2 month visit. Following the 2 month visit through end of study participation, reporting requirements change to concomitant medications associated with reportable AEs only (vascular access related AEs and SAEs). All concomitant medications, whether prescription or non-prescription (including pharmacological doses of vitamins) with the exception of medications listed below, are to be recorded in the eCRF, using the brand name and stating dosage, indication and duration of intake.

The following medications DO NOT need to be recorded in the eCRF:

- Standard medications and IV fluids typically required for sedation, induction and maintenance of anesthesia during product implantation procedure
- Medications given during routine dialysis treatments (e.g., normal saline, hypertonic saline, etc.)

Antibiotics given, as prophylaxis for the AV fistula surgery must be recorded.

### 9.7.1. Prohibited Concomitant Medication

The following concomitant medications/therapies are *prohibited*:

- Intra-surgical use of non-removable hemostats (fibrin glue, etc.)

## 9.8. Treatment Compliance

The Sirolimus-eluting Collagen Implant is a single-use intra-operative implant, administered by the surgical investigator. Treatment compliance is not applicable for this study.

# 10. ASSESSMENT OF EFFICACY

## 10.1. Primary Endpoint

The primary endpoint of the study is Fistula Suitability for Dialysis at 6 months (FSD6) defined as a composite of:

- a. For subjects who are on hemodialysis by day 150, suitability for dialysis will be determined by the ability to use the fistula for dialysis using 2-needles with a mean dialysis machine blood pump speed of  $\geq 300$  mL/min for at least two-thirds of the dialysis sessions performed during a 30 day suitability ascertainment period that will commence on day 150.
- b. For subjects who are not on hemodialysis on day of enrollment and who do not initiate hemodialysis by day 150, suitability for dialysis will be determined by a vascular ultrasound performed at the 6 month follow up visit. Suitability for dialysis

will be defined as a fistula with an access vein diameter (AVD) of  $\geq 6$  mm (internal diameter) and an access blood flow of  $\geq 500$  mL/min.

Evaluation of Fistula Suitability for Dialysis at 6 months:

- For subjects undergoing hemodialysis during the suitability ascertainment period, suitability for dialysis will be based on the subject's dialysis session records
- For subjects who are not on hemodialysis on the day of enrollment (i.e. on the day of fistula creation) and who do not initiate hemodialysis by day 150, suitability for dialysis will be based on duplex ultrasound results performed at the 6 month follow up visit.

## **10.2. Secondary Endpoints**

### **10.2.1. Fistula Suitability for Dialysis at 12 months**

Fistula Suitability for Dialysis at 12 months (FSD12), defined as a composite of

- a. For subjects who are on hemodialysis by day 330, suitability for dialysis will be determined by the ability to use the fistula for dialysis using 2-needles with a mean dialysis machine blood pump speed of  $\geq 300$  mL/min for at least two-thirds of the dialysis sessions performed during a 30 day suitability ascertainment period that will commence on day 330.
- b. For subjects who are not on hemodialysis on day of enrollment and who do not initiate hemodialysis by day 330, suitability for dialysis will be determined by a vascular ultrasound performed at the 12 month follow up visit. Suitability for dialysis will be defined as a fistula with an access vein diameter (AVD) of  $\geq 6$  mm (internal diameter) and an access blood flow of  $\geq 500$  mL/min.

### **10.2.2. Fistula Maturation by Day 90**

Fistula Maturation by Day 90, defined as a composite of:

- a. For subjects who are on hemodialysis by day 90:
  - Three consecutive dialysis sessions using 2-needles with a mean dialysis machine blood pump speed of  $\geq 300$  mL/min, the first of these three dialysis sessions completed on or before 90 days from the time of creation of the AV fistula, or
  - Two-needle dialysis on or before 90 days with no further use of the catheter prior to achieving three consecutive dialysis sessions using 2-needles with a mean dialysis machine blood pump speed of  $\geq 300$  mL/min.
- b. For subjects who do not initiate hemodialysis by day 90, fistula access vein diameter (AVD) of  $\geq 6$  mm (internal diameter) and an access blood flow of  $\geq 500$  mL/min determined by a vascular ultrasound performed at the 3-month follow up visit.

Evaluation of Fistula Maturation is based on subject's dialysis session records

### **10.2.3. Secondary Patency**

Secondary patency, defined as the interval from the time of access placement until access abandonment.

Secondary patency will be evaluated based on

- Clinical evaluation of the fistula,
- Subject's dialysis session records (for subjects who are undergoing hemodialysis),
- Imaging results (Duplex ultrasound and/or angiogram - if applicable and available), and,
- Access event data.

### **10.2.4. Re-intervention Rate**

Re-intervention rate is defined as the total number of vascular access interventions performed during study participation to maintain or re-establish patency of the index fistula, as well as interventions to assist fistula maturation divided by the total subject participation time in the study. It is expressed as number of interventions per subject-year of exposure. Abandonment of the index fistula will count for one intervention.

If a subject's index fistula is abandoned and the subsequent subject follow-up is incomplete, that subject's participation time will be censored at the time follow-up begins to be incomplete. Each subject's follow-up time will be determined PRIOR to database lock and unblinding.

Re-intervention rates will be calculated 6 months and 12 months following fistula creation. Duration of fistula evaluation is defined as the time from fistula creation to end of study, fistula abandonment, or upon reaching a censored event.

## **10.3. Tertiary Endpoints**

### **10.3.1. Time To First Dialysis (TTFD)**

Time To First Dialysis (TTFD) is defined as the time from fistula creation to the time when the fistula can support three consecutive dialysis sessions using 2-needles with a mean dialysis machine blood pump speed of  $\geq 300$  mL/min.

TTFD will be calculated as the time to first of three consecutive dialysis sessions meeting the above defined criteria and will be evaluated only for subjects who are on dialysis at the time of study enrollment or those who initiate dialysis on or before 28 days from the time of the AV fistula procedure.

The evaluation of TTFD will be based on the subject's dialysis session records.

### **10.3.2. Fistula Suitability for Dialysis at 6 months with preserved primary patency**

Fistula suitability for Dialysis at 6 months with preserved primary patency, defined as a composite of

- a. For subjects who are on hemodialysis by day 150, suitability for dialysis will be determined by the ability to use the fistula for dialysis using 2-needles with a mean dialysis machine blood pump speed of  $\geq 300$  mL/min for at least two-thirds of the dialysis sessions performed during a 30 day suitability ascertainment period that will commence on day 150.
- b. For subjects who are not on hemodialysis on day of enrollment and who do not initiate hemodialysis by day 150, suitability for dialysis will be determined by a vascular ultrasound performed at the 6 month follow up visit. Suitability for dialysis will be defined as a fistula with an access vein diameter (AVD) of  $\geq 6$  mm (internal diameter) and an access blood flow of  $\geq 500$  mL/min.

Primary Patency is defined as freedom from the first occurrence of access thrombosis or an intervention performed to maintain or re-establish access patency or assist fistula maturation.

Evaluation of Fistula Suitability for Dialysis at 6 months with preserved primary patency:

- Subject's dialysis session records (for subjects who are undergoing hemodialysis),
- 6 month duplex ultrasound results for subjects whose index fistula is not in use for hemodialysis on day 150, and,
- Access event data.

### **10.3.3. Fistula Suitability for Dialysis at 12 months with preserved primary patency**

Fistula suitability for Dialysis at 12 months, defined as a composite of

- c. For subjects who are on hemodialysis by day 330, suitability for dialysis will be determined by the ability to use the fistula for dialysis using 2-needles with a mean dialysis machine blood pump speed of  $\geq 300$  mL/min for at least two-thirds of the dialysis sessions performed during a 30 day suitability ascertainment period that will commence on day 330.
- d. For subjects who are not on hemodialysis on day of enrollment and who do not initiate hemodialysis by day 330, suitability for dialysis will be determined by a vascular ultrasound performed at the 12 month follow up visit. Suitability for dialysis will be defined as a fistula with an access vein diameter (AVD) of  $\geq 6$  mm (internal diameter) and an access blood flow of  $\geq 500$  mL/min.

Primary Patency is defined as freedom from the first occurrence of access thrombosis or an intervention performed to maintain or re-establish access patency or assist fistula maturation.

Evaluation of Fistula Suitability for Dialysis at 12 months with preserved primary patency:

- Subject's dialysis session records (for subjects who are undergoing hemodialysis),
- 12 month duplex ultrasound results for subjects whose index fistula is not in use for hemodialysis on day 330, and,

- Access event data.

#### **10.3.4. Primary Patency**

Primary Patency, defined as the interval from the time of fistula creation until the first occurrence of fistula thrombosis or an intervention performed to restore/maintain patency.

The following events will NOT cause loss of primary patency:

- Intervention to ligate or occlude collateral veins,
- An invasive angiogram without an intervention (i.e., diagnostic study only),
- Procedures performed to treat steal syndrome.

Evaluation of Primary patency will be based on one or more of the following:

- Clinical evaluation of the fistula,
- Subject's dialysis session records (for subjects who are undergoing hemodialysis),
- Access event data.

### **10.4. Additional Definitions**

#### **10.4.1. Mean Dialysis Machine Blood Flow**

Mean dialysis machine blood flow is defined as the mean of all blood flow measurements recorded after the first 30 minutes and prior to the last 30 minutes of the dialysis session. Dialysis machine blood flow (mL/min) will be obtained from the dialysis unit's electronic or paper records. Measurements made during the first 30 minutes of a dialysis session will be excluded from the determination of the mean dialysis machine blood flow since the pump speed is often increased gradually during the early portion of the dialysis session. Measurements obtained during the last 30 minutes of the dialysis session will be excluded from the determination of the session mean pump speed since the pump speed may be decreased due to fluctuations in blood pressure or in preparation for discontinuing the dialysis session.

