## **11. ASSESSMENT OF SAFETY**

Safety evaluations will be based on treatment emergent adverse events (TEAEs) up to the 2 month visit and vascular access events reported during the study. Treatment emergent is defined as any adverse event that emerges after the subject is enrolled (run-in and randomized) in the study. The run-in subjects' adverse events will be included in the safety evaluation. Vascular access events include access dysfunction, thrombosis, access-related hand ischemia, infiltration requiring a rest period, fistula-related bleeding, infection, problems with wound healing, aneurysm, pseudoaneurysm, and all interventional procedures performed on the study fistula. During follow-up, after the 2 month visit, the following will be reported and recorded: vascular access events, concomitant medications and therapies associated with vascular access, serious adverse events (SAEs) and AEs reported during an SAE. At each follow-up visit up to the 2 month visit, AEs and concomitant medications will be recorded. Changes in comparison to baseline and the 2 month visit that are considered to be clinically significant will be reported as AEs.

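### The last-30-minute exclusion applies whatever ended the session, so a two-needle session stopped because the fistula failed can still score as meeting 300 mL/min

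*Combined protocol and SAP*

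**What the plan says.** Section 10.4.1 defines the session value as the "mean of all blood flow measurements recorded after the first 30 minutes and prior to the last 30 minutes of the dialysis session". Early readings are left out "since the pump speed is often increased gradually during the early portion of the dialysis session". Late readings are left out because "the pump speed may be decreased due to fluctuations in blood pressure or in preparation for discontinuing the dialysis session". Neither exclusion depends on how long the session lasted, whether it was completed, or why it stopped.

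Limb (a) of the primary endpoint (Section 10.1) requires the "ability to use the fistula for dialysis using 2-needles with a mean dialysis machine blood pump speed of" at least 300 mL/min "for at least two-thirds of the dialysis sessions performed during a 30 day suitability ascertainment period that will commence on day 150". For these subjects, "suitability for dialysis will be based on the subject's dialysis session records". FSD12 (Section 10.2.1) uses the same rule from day 330. Day 90 maturation (Section 10.2.2) and Time To First Dialysis, TTFD (Section 10.3.1), use the same session mean over three consecutive sessions.

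None of these sections sets a minimum session length, a completion requirement or a minimum number of readings. Section 11 lists "infiltration requiring a rest period" among the vascular access events but does not link such events to the scoring of a session.

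**The concern.** The end exclusion makes sense when a falling pump speed says nothing about the access. When a session is stopped because the fistula infiltrates or loses flow, a fall in the last half hour is the evidence of failure, and the rule removes it. What remains is the part of the session in which the fistula still worked.

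The session mean feeds the primary endpoint, two secondary endpoints and a tertiary endpoint. The protocol requires at least 100 of about 200 evaluable subjects to be on hemodialysis at the index procedure, and others join limb (a) if they start by day 150. Session scoring therefore decides FSD6 for a large part of the cohort. If the scoring of access-terminated sessions is left open, it may be settled case by case during data review.

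**Working it through.** The plan gives no figure for this point. Its FSD6 power figure is reproduced in step 5 for scale only.

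**1. Scored window.** For a session of L minutes the window is L − 60 minutes: 30 at L = 90, 60 at L = 120, 90 at L = 150, and none at L ≤ 60. Sparse charting widens the gap. With readings every 30 minutes and strict boundaries, a 90-minute session has no eligible reading.

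**2. Example sessions.** Assumptions not in the documents: readings every 15 minutes, 350 mL/min until the final 30 minutes, then 150 mL/min until the session is stopped.

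| Stopped at (min) | Mean under 10.4.1 | Mean with no end exclusion |
|---|---|---|
| 60 | none | 150 |
| 90 | 350 | (2×350 + 2×150)/4 = 250 |
| 120 | 350 | (4×350 + 2×150)/6 = 283 |
| 150 | 350 | (6×350 + 2×150)/8 = 300 |

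At 90 and 120 minutes the exclusion turns a failing session into a passing one. At 150 minutes the session passes either way, so dropping the exclusion would not be enough. The missing piece is a rule for how an access-terminated session counts.

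**3. FSD6 and FSD12.** Assume three sessions a week: 30 × 3/7 = 12.9, so 12 or 13 sessions.
- 13 sessions: two-thirds of 13 is 8.67, so 9 are needed. Seven good sessions plus two credited access-terminated ones move 7/13 = 53.8% (failure) to 9/13 = 69.2% (success).
- 12 sessions: 8 are needed. The same two sessions move 6/12 = 50.0% to 8/12 = 66.7%.

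A subject well above or below the cut-off does not change status.

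**4. Three-session endpoints.** If two good sessions are followed by an access-terminated session that is credited, the run is complete. If it is not credited, a new run can start no earlier than the next session. TTFD then moves by at least three sessions, or one week at three per week. Day 90 status changes only if no later qualifying sequence meets the Day 90 definition.

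**5. Scale for FSD6.** With n = 100 per arm, 45% versus 65%, two-sided 0.05 and pooled variance under the null:

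Φ{[0.20 − 1.96 × √(2 × 0.55 × 0.45/100)] / √[(0.45 × 0.55 + 0.65 × 0.35)/100]} = Φ(0.0621/0.0689) = 81.6%.

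This agrees with the plan's approximately 82%. Now suppose a fraction f of truly unsuitable subjects is scored suitable, so that a rate p becomes p + (1 − p)f. The documents give no f.
- Equal f in both arms: power is 80.2% at f = 2%, 77.9% at 5% and 74.0% at 10%.
- f = 5% in control only: 47.75% versus 65%, a difference of 17.25 points.
- f = 5% in treatment only: 45% versus 66.75%, a difference of 21.75 points.

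The sign of the effect depends on where the affected sessions fall.

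**The case against.** **Direction.** A reader might infer that the rule favours control, which is expected to have more dysfunctional fistulas, and so dilutes the treatment difference. The documents do not support this. A session is wrongly credited only if it has two-needle use, lasts more than 60 minutes and has a mid-session mean of at least 300 mL/min. Very poor fistulas produce no such sessions. At the planning rates the treatment arm may have more fistulas in use, and so more sessions exposed.

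**Very short sessions.** A reader might also infer that a session of 60 minutes or less drops out, turning 8/13 (61.5%, failure) into 8/12 (66.7%, success). Read literally, Section 10.1 does not allow this. The session was performed, and without a mean it cannot be shown to reach 300 mL/min, so it stays in the denominator as not meeting and the result remains 8/13. This needs confirmation only.

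**Catheter conversion.** The exclusion is tied to the end of the session, not the end of fistula use. If dialysis continues by catheter for 30 minutes or more, the discarded minutes are catheter minutes and the failing fistula readings are kept. Such a session also does not plainly meet the two-needle requirement. This objection stands. The difficulty there is that no scoring rule exists for a converted session.

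**Ability to use the fistula.** This phrase could be read to fail an aborted session, but no operational rule says so.

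**The SAP.** Section 13.1 says the SAP holds the derivation algorithms, and no such text is in the supplied document. A rule may exist there. However, Section 10.4.1 is an explicit definition, so an SAP rule that departs from it would still need the two texts reconciled.

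**Self-correction.** A fistula rested after infiltration tends to lose later sessions as well, so the two-thirds rule partly protects FSD6. That is fair, and it protects the three-session endpoints less.

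**Conclusion.** The point holds in a limited form. As written, Section 10.4.1 can credit a two-needle session of more than 60 minutes that was stopped because of the index fistula, after discarding its last 30 minutes. Crediting also requires the remaining readings to average at least 300 mL/min, so it is possible and not certain.

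The effect on FSD6 and FSD12 is confined to subjects near two-thirds (7/13 to 9/13, assuming 13 sessions). For Day 90 maturation and TTFD a single session can matter. The 13 sessions, the reading pattern and f are assumptions. The documents give no rate of access-terminated sessions, so neither the frequency nor the direction of any bias between arms can be determined, and the power figures in the working are not estimates of actual loss. The plan's own power figure is not in question. This is a cheap improvement.

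**What to change.** In Section 10.4.1 and the SAP, state the following:

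- A session ended early, or converted to a catheter or single needle, because of the index fistula counts as performed and as not meeting the criterion, whatever its trimmed mean. The reason is taken from the session record or from a recorded vascular access event.
- A session with no eligible reading stays in the denominator as not meeting. This confirms the literal reading of Section 10.1.
- Both rules apply to FSD6, FSD12, Day 90 maturation and TTFD, and sessions are classified blind to treatment.

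The exclusion stays in place for all other sessions. Sessions ended for a non-access reason should not be removed from numerator and denominator, because that would let a judged reason alter a record-based endpoint.

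The cost is slightly more abstraction and a slightly lower success rate in both arms. Run sheets are already source documents (Section 14.1), and vascular access events are recorded throughout (Sections 11 and 12.2.1). The documents do not say that run sheets record why a session ended, which is why either source is accepted. The change concerns scoring only and does not affect how dialysis is delivered.
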